1.0 Objectives/ Specific Aims

Our study aims to compare the efficacy of a deep-layer, knotless closing method using the Dermabond PRINEO skin closure device (2-octyl cyanoacrylate adhesive glue in combination with self-adhesive polyester mesh tape) to the current practices of wound closure after total joint arthroplasty. While surgeons utilize a variety of incision closure techniques, most use a layered closure with deep fascial closure consisting of interrupted, knotted sutures combined with either staples (Figure 1) or sutures (Figure 2) for superficial closing. In this Phase 4 clinical trial, we hypothesize that the Dermabond PRINEO wound closure system with running knotless sutures for deep and superficial closure (Figure 3) will significantly reduce closure time in the operating room and achieve similar or better incision healing after shoulder arthroplasty.

Primary aims:

1.1 Aim 1: To quantify differences the time required for wound closure with the PRINEO closure method (Figure 3) and that of traditional closure methods (interrupted deep fascial suture with either subcuticular sutures and traditional Dermabond (Figure 2) or metal staples for superficial closure (Figure 1)

H_0 : There are no differences in wound closure times between PRINEO and subcuticular sutures or metal staples in time to close incisions

H_A : There are differences between PRINEO and subcuticular sutures or metal staples in time to close incisions such that staples will be significantly faster than PRINEO and PRINEO will be significantly faster than sutures.

1.2 Aim 2: To quantify differences between PRINEO and subcuticular sutures or metal staples in wound healing over three postoperative follow-up points

H_0 : There are no differences between PRINEO and subcuticular sutures or metal staples in wound healing (dehiscence and drainage) over three postop follow-up points.

H_A : There are differences between PRINEO and subcuticular sutures or metal staples in wound healing (dehiscence and drainage) over three postop follow-up points such that PRINEO demonstrates superior healing to both sutures and staples.

Exploratory Aims:

1.3 Aim 3: To quantify differences between PRINEO and subcuticular sutures or metal staples in observer-evaluated and patient-evaluated cosmetic outcomes for the surgical scar over four postoperative follow-up points

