4.0 Study Endpoints

The duration of wound closure is primary endpoint for this study. Wound closure timing outcomes will be collected in the operating room towards the conclusion of each surgery. Closure time is the time between the first stitch for closure and the completion of application of dressing to the wound. The incision length will be measured to calculate time per centimeter.

Cost per minute of operation time is another endpoint for the study. It will be conservatively approximated using existing reports of personnel capacity rates for orthopaedic surgeon. Cost-effectiveness analysis will be conducted by comparing the total cost of all wound closure materials for each technique, and a cost per minute applied to wound closure time.

Wound outcomes, both clinical and cosmetic, will be another primary endpoint for this study. Patient-centered outcomes for wound and scar evaluation will be collected at 6 weeks and 3 month postoperative appointments in clinic. These outcomes will be measured using the Modified Hollander Cosmesis Scale [14, 21], the Patient and Observer Scar Assessment Scale (POSAS) [14, 22, 23], and the Acute Inflammatory Response Evaluation (AIRE) score as described in the 2015 study by Blondeel et al [14].

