2. Total time for wound closure in minutes and seconds, from the first stitch for closure to the application of wound dressing.
3. The incision length in centimeters

4. The cost of materials utilized for wound closure (suture, Dermabond, PRINEO, staples, dressings, etc.)

All patients will be seen in clinic 2 weeks post operatively during which time the wound closure technique (sutures, or staples) will be removed by a nurse according to the manufacturer and standard technique. The patients who are randomized to Dermabond PRINEO will be instructed to keep their polymer mesh on for an additional 2 weeks after their 2 weeks visit. Any complications such as drainage, acute inflammation, or signs of infection will be recorded at this time and treated per clinical standards. The following data points to measure wound clinical and cosmetic outcomes, will be collected at 6 weeks and 3 months postoperatively:

1. mHCS score
2. AIRE score
3. POSAS score
4. Complications and adverse events

mHCS, AIRE, and POSAS scores are all dependent on aspects of the physical exam, such as evaluation of pliability, temperature, edema, pain, and contour. To mitigate any observer bias, all incisions will be photographed and additionally evaluated by a plastic surgeon ([name]) blinded to the treatment condition using the POSAS-Observer characteristics which may be assessed through standardized photography alone (Vascularity, Pigmentation, Thickness, Relief, Surface Area, and Overall Opinion).

A medical record review will also be performed to collect the following data: Age; gender; BMI (including height and weight), race, diabetes status (type, insulin dependency, years diagnosed); history of smoking/tobacco use; frequency of alcohol consumption.

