Upon enrollment, patients will be assigned unique identifiers to be used in statistical analysis. Enrollment logs, data sheets and photographs will be electronically stored within a MUSC password protected secured computer, in a MUSC supported password-protected digital folder, accessible only to the members of the research team. Copies of consent forms, visit report forms, and adverse event forms will be stored in a locked cabinet in a locked room on the Medical University of South Carolina campus in downtown Charleston, SC. If a patient has a unique, identifying tattoo near his/her incision site, the tattoo will be avoided during photographing or blurred out digitally before storage. If the tattoo is within 2 inches of the site and therefore difficult to avoid or blur without compromising the image quality of the wound, the patient will be excluded from the study.

Data analysis plan:

Data from patients' medical records to be included in the data sheet to include as covariates during data analysis will include age, gender, BMI, race, diabetes status, history of smoking/tobacco use, and alcohol consumption. The differences in mHCS, AIRE, and POSAS scores between treatment groups will be tested through ANOVA tests and subsequent Tukey-HSD post-hoc tests, and difference in complication rates will be evaluated by Chi-square tests. Analysis will be conducted on MUSC registered computers through IBM SPSS 25.0.

12.0 Provisions to Monitor the Data to Ensure the Safety of Subjects (if applicable)

Adverse events will be collected at follow up visits and PI will review them regularly and report them per MUSC IRBs policy.

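### The plan's only blinded outcome assessment does not reach dehiscence or drainage, the two outcomes that define primary Aim 2

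*Combined protocol and SAP*

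**What the plan says.** **The aims (Section 1.0).** Aim 2 is listed as primary. Its null hypothesis is that the closure methods do not differ "in wound healing (dehiscence and drainage) over three postop follow-up points"; its alternative is that PRINEO heals better than both controls. Aim 3, listed as exploratory, looks for differences "in observer-evaluated and patient-evaluated cosmetic outcomes for the surgical scar over four postoperative follow-up points".

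**The endpoints (Section 4.0).** Here the hierarchy is different: "Wound outcomes, both clinical and cosmetic, will be another primary endpoint for this study". The measures named are the mHCS, POSAS and AIRE scores.

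**The blinded read (Section 10.0).** The protocol acknowledges observer bias and has every incision photographed and read by a plastic surgeon "blinded to the treatment condition using the POSAS-Observer characteristics which may be assessed through standardized photography alone". The items are "Vascularity, Pigmentation, Thickness, Relief, Surface Area, and Overall Opinion".

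**How healing events are captured.** For the 2-week visit Section 10.0 says: "Any complications such as drainage, acute inflammation, or signs of infection will be recorded at this time". Complications and adverse events are collected again at 6 weeks and 3 months. Dehiscence is not named in these lists, and neither the recorder nor any masking is stated. Section 12.0 adds: "Adverse events will be collected at follow up visits and PI will review them regularly".

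**Who is likely to know the arm.** Section 5.0 includes patients who expect follow-up care from their operating surgeon. At 2 weeks a nurse removes sutures or staples, while the PRINEO mesh stays on for two more weeks (Section 10.0). The patient is masked only until the first follow-up visit or dressing removal.

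**Analysis (Section 11.0).** Chi-square tests are named for complication rates. No test is named for Aim 2.

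**The concern.** The plan identifies observer bias and sets up a remedy, but the remedy stops short of an outcome it calls primary. Minor wound-edge separation and minor drainage are matters of judgement, and the plan defines neither. Whoever records them probably knows which closure was used. They also work under a protocol whose alternative hypothesis favours PRINEO and whose rationale (Section 10.0) says PRINEO very likely removes the risk of dehiscence.

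If borderline findings are recorded less readily in PRINEO patients, a healing advantage could appear in the clinic record with no independent source to check it against. Groups are small, so a few such calls matter. Closure time, the outcome used to size the trial, is not affected.

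**Working it through.** **1. The plan's own figure.** The only computed sample size is for closure time. With d = 0.93, two-sided alpha 0.05 and power 0.80, the normal approximation gives n = 2 × (1.960 + 0.842)² / 0.93² = 15.70 / 0.865 = 18.15, rounded up to 19 per group, or 4 × 19 = 76. This reproduces Section 11.0. It says nothing about Aim 2, for which the plan gives no event rate and no power calculation.

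**2. Aim 2 set against the blinded read.**

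| Outcome | Status | On the blinded read? |
|---|---|---|
| Dehiscence | Primary (Aim 2) | No |
| Drainage | Primary (Aim 2); also part of Aim 4 | No |
| Six POSAS-Observer items | Exploratory (Aim 3); primary on the Section 4.0 wording | Yes |
| mHCS, AIRE | Primary on the Section 4.0 wording | No; clinic scores that depend on physical examination |

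The conflict between Sections 1.0 and 4.0 changes the status of the scar items. It does not bring dehiscence or drainage into the blinded read.

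**3. Weight of one patient.** With 22 per group (Section 6.0), 1/22 = 4.5 percentage points.

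**4. Sensitivity of a test to one call.** For 0/22 v k/22 events:
- Pearson chi-square = 44 × (22k)² / [22 × 22 × k × (44 − k)].
- The continuity-corrected version replaces (22k)² by (22k − 22)².
- Two-sided Fisher p = 2 × C(22,k) / C(44,k).

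| Events | Pearson (p) | Corrected (p) | Fisher p |
|---|---|---|---|
| 0 v 3 | 3.22 (0.073) | 1.43 (0.232) | 2 × 1,540 / 13,244 = 0.233 |
| 0 v 4 | 4.40 (0.036) | 2.48 (0.116) | 2 × 7,315 / 135,751 = 0.108 |

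Going from 3 to 4 events crosses 0.05 only with the uncorrected Pearson test. At 0 v 4 the smallest expected count is 22 × 4/44 = 2, too small to rely on that version.

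**5. Illustration under assumed rates.** Assume equal true event rates in both arms, with half of PRINEO events going unrecorded. The probability that a two-sided 5% uncorrected chi-square test rejects is the sum of binomial probabilities over all tables with |a − b|/n ÷ √[2p̄(1 − p̄)/n] > 1.96, where a and b are the event counts, n is the number per arm and p̄ = (a + b)/(2n).

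| True rate (assumed) | 22 v 22: no bias → bias | 44 v 44: no bias → bias |
|---|---|---|
| 5% | 1.5% → 1.4% | 4.8% → 6.9% |
| 10% | 4.3% → 6.5% | 5.9% → 15.9% |
| 20% | 5.2% → 15.2% | 5.4% → 27.1% |

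The effect runs from none to substantial, depending entirely on the assumed rate and the assumed under-recording.

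**The case against.** **Unblinded assessment is not stated.** A reader might infer that the plan assigns Aim 2 solely to unblinded staff. It does not: no recorder is named and nothing is said about that person's masking. The statement that the PI reviews adverse events does not settle who judges dehiscence. This objection stands as to wording. The inference is still strong, since a surgeon who performed the closure knows the arm and at 2 weeks the closure is visible to anyone. It is weaker at 6 weeks and 3 months for other staff, when the closure materials should be off.

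**The blinded read may serve a primary endpoint.** A reader might infer that blinding was spent only on an exploratory scale. On the Section 4.0 wording the POSAS read does reach a primary endpoint, so that contrast cannot be pressed. The gap for dehiscence and drainage remains.

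**The more basic gap is definition.** Aim 2 has no event definition and no named analysis, and moving an undefined judgement to another reader would not cure that. This stands, and any added item needs a definition.

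**Photographs cannot carry the aim.** At 2 weeks the mesh would reveal the arm, early events may have healed by 6 weeks, and drainage is mostly a matter of history. This also stands. It argues against replacing the clinic record with late photographs, but not against using them as a check.

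**Conclusion.** The point holds in a limited form. The blinded read does not reach dehiscence or drainage, no masking is described for whoever records them, and the arm is very probably known to that person. A primary aim is therefore open to observer bias that the plan already recognises elsewhere.

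One reclassified patient is worth 4.5 points in a group of 22. Beyond that, no size can be given: the documents contain no dehiscence or drainage rate, and at an assumed 5% rate with 22 v 22 even halved recording in PRINEO patients does not raise the rejection rate.

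A reader might infer that a single borderline call would make the planned analysis significant. The documents do not support this. Chi-square is assigned to complication rates, which under Aim 4 include drainage but not dehiscence, and the crossing from 3 to 4 events disappears with Fisher's test or a continuity correction.

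The conclusion rests on two assumptions: that follow-up takes place with the operating surgeons as Section 5.0 expects, and that no masking procedure exists outside the document.

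**What to change.** **Section 10.0.** State at which visits photographs are taken; the text implies 6 weeks and 3 months but does not say so. Add two yes/no items, each with a written definition, to the same blinded reader's form at those visits: wound-edge separation present, and visible discharge present. Redness should not be added for this purpose, since inflammation belongs to Aim 4. State who records dehiscence and drainage in clinic and whether that person knows the arm.

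**Section 11.0.** Keep the clinic record as the source for Aim 2 across all visits. Report the blinded separation and discharge results beside it as a pre-specified check, with the between-arm comparison by Fisher's exact test. State in advance that a PRINEO advantage seen only in the clinic record will be interpreted as open to observer bias.

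**Sections 1.0 and 4.0.** Reconcile whether cosmetic outcomes are primary or exploratory.

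**Cost.** Two tick-boxes and their definitions, with a reader and photographs already planned and no new staff. The protection is partial: findings at 2 weeks, events healed before 6 weeks and most drainage will still rest on the clinic record, and the report should say so.

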11.0 Data Management

Justification of sample size:

The Cohen's effect size of 0.93 corresponds to a difference of means of 7.5 minutes with a pooled standard deviation of 8 minutes. The PI has determined that a difference of 10 minutes will be the minimum significant difference for clinical and economic relevance. 5 minutes alternatively would be an irrelevant amount of time savings. Therefore, designing the investigation to detect 7.5 minutes would ensure that we would determine if 10 minutes difference exists between the different wound closure techniques.

Economically, at an estimated cost of \$30 per minute of operative time [24], this corresponds to \$300 saved per procedure. Ten fewer minutes of operative time across six consecutive shoulder arthroplasties would save an hour total of operative time, which allows for the possible inclusion of a seventh surgery in the operative room schedule.

In our study, differences in time to closure between the groups will be compared by two-sample T-tests for independent means. With a Cohen's effect size of 0.93, a standard

alpha of 0.05 to determine statistical significance, and a target power of 0.80, an apriori power analysis indicates 76 total for the sample size, or 19 per group. A sample size of 88 total patients, with 22 in each group (two parallel treatment arms and two distinct control arms each representing surgeon's choice), will ensure sufficient power to detect economically relevant, statistically significant differences in time to closure outcomes between the three wound closure methods, while leaving room to accommodate patients who withdraw from the study or are lost to follow up.

Data storage and management:

As multiple data points will be collected for each patient over the course of their treatment, an enrollment log will be established, assigning patients unique identifiers, and a data sheet will be started where the total operating time, the wound closure time, the cost of wound closure, and the incision length will be recorded. Furthermore, the mHCS score, the AIRE score, the POSAS scores, and complications will be recorded in this data sheet for each postoperative visit to the clinic (at 6 weeks and 3 months).

Upon enrollment, patients will be assigned unique identifiers to be used in statistical analysis. Enrollment logs, data sheets and photographs will be electronically stored within a MUSC password protected secured computer, in a MUSC supported password-protected digital folder, accessible only to the members of the research team. Copies of consent forms, visit report forms, and adverse event forms will be stored in a locked cabinet in a locked room on the Medical University of South Carolina campus in downtown Charleston, SC. If a patient has a unique, identifying tattoo near his/her incision site, the tattoo will be avoided during photographing or blurred out digitally before storage. If the tattoo is within 2 inches of the site and therefore difficult to avoid or blur without compromising the image quality of the wound, the patient will be excluded from the study.

Data analysis plan:

Data from patients' medical records to be included in the data sheet to include as covariates during data analysis will include age, gender, BMI, race, diabetes status, history of smoking/tobacco use, and alcohol consumption. The differences in mHCS, AIRE, and POSAS scores between treatment groups will be tested through ANOVA tests and subsequent Tukey-HSD post-hoc tests, and difference in complication rates will be evaluated by Chi-square tests. Analysis will be conducted on MUSC registered computers through IBM SPSS 25.0.

12.0 Provisions to Monitor the Data to Ensure the Safety of Subjects (if applicable)

Adverse events will be collected at follow up visits and PI will review them regularly and report them per MUSC IRBs policy.

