3.0 Intervention to be studied

Specifically, in the 510(k) cleared Dermabond PRINEO skin closure system (Ethicon Inc.), the 2-octyl cyanoacrylate adhesive is used in combination with a polyester mesh tape, either 22cm or 60cm in width. This mesh tape is designed to provide for tighter sealing of the incision and may further protect against discharge in more mobile wounds. Use of the tape may strengthen the wound closure and also simplify and improve alignment and apposition of wound edges [[12] and Ethicon internal testing]. Several prospective randomized, controlled trials have demonstrated consistently lower wound closing times and equivalent or significantly improved cosmetic outcomes and complication rates with this system [13-16]. More flexibility in application due to “body-contouring” has also been noted [17].

Observational studies of the PRINEO system report success use of the device as evaluated by surgeon and patient satisfaction [11, 17, 18]. Research of the PRINEO system used after total joint replacement are at present limited to retrospective studies [11, 18] and case reports of allergic reactions [19, 20].

[name] currently closes incisions after shoulder arthroplasty with metal staples, and [name] currently closes incisions after shoulder arthroplasty using subcuticular sutures with Dermabond. Both surgeons use interrupted deep-layer sutures. This study will consist of two parallel comparisons to these distinct control arms. The PRINEO closing method, which utilizes running deep and superficial sutures with Dermabond PRINEO, will be directly compared to each surgeon’s wound closure technique, as half of each surgeon’s patients will be randomized to the PRINEO treatment condition while the other half continue to undergo wound closure with the current technique utilized by the

surgeon. This will result in two parallel treatment arms and two distinct control arms (Fig. 1). Both surgeons have significant experience in the application of Dermabond PRINEO for wound closure.

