6.0 Number of Subjects

A total of 88 patients, with 22 in each treatment group, will be enrolled. With a treatment and control arm for each surgeon, this results in a total of 44 patients in a treatment arm and 44 in a control.

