10.0 Study Design/ Methods

Randomization will take place the morning of surgery based on a randomly organized, computer-generated order.

Patients in [name] clinic will be randomized to one of two treatment conditions for wound closure after shoulder arthroplasty: 1) deep layer closure with 0-0 vicryl interrupted sutures followed by superficial skin closure with metal staples with aquacel dressing and 2) deep layer closure with a running 2-0 unidirectional Stratafix suture followed by superficial closure with subcuticular bidirectional 3-0 Stratafix suture followed by the Dermabond PRINEO (60cm or 22cm polyester mesh and 2-octyl cyanoacrylate adhesive) with Medipore and folded 4x4 cotton gauze dressing.

Patients in [name] clinic will be randomized to one of two treatment conditions for wound closure after shoulder arthroplasty: 1) deep closure with interrupted 2-0 vicryl sutures followed by a running subcuticular bidirectional 3-0 Stratafix with Dermabond and Medipore dressing with folded 4x4 cotton gauze dressing and 2) deep layer closure with a running 2-0 unidirectional Stratafix suture followed by superficial closure with subcuticular bidirectional 3-0 Stratafix suture followed by the Dermabond PRINEO (60cm or 22cm polyester mesh and 2-octyl cyanoacrylate adhesive) with Medipore and folded 4x4 cotton gauze dressing.

The rationale for investigating the current practice of deep closure with interrupted sutures is as follows: Using running suture introduces a potential risk of wound dehiscence if the suture fails at any juncture despite the presence of the barbs. The Dermabond PRINEO represents a powerful closure mechanism that in all probability eliminates the risk of wound dehiscence regardless of the skin closure method. Therefore, using a rapid wound closure method with deep layer running sutures is now a possibility with the Dermabond PRINEO that was not available before.

Patients will not be made aware of the treatment they are randomized to until their first follow up visit or when wound dressing is removed to reveal the device used for wound closure.

At the conclusion of the surgery, the assigned wound closure technique will be implemented. The following data points to measure the primary outcome, wound closure efficiency, will be collected in the operating room:

1. Total operating time in minutes and seconds, from the first incision to the application of wound dressing.

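### The all-pairs Tukey analysis of the wound and scar scores does not isolate the two within-surgeon randomised contrasts; four of its six pairs compare surgeons, and the randomised pairs lose power

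*Combined protocol and SAP*

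**What the plan says.** Section 3.0 sets out the design: "This study will consist of two parallel comparisons to these distinct control arms". The split is 1:1 under each operator: "patients will be randomized to the PRINEO treatment condition while the other half continue to undergo wound closure with the current technique", meaning that operator's own control method. Section 10.0 repeats this for each surgeon separately: patients in that "clinic will be randomized to one of two treatment conditions for wound closure after shoulder arthroplasty". One clinic has staples or PRINEO, and the other has subcuticular sutures or PRINEO.

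On numbers, section 6.0 says "A total of 88 patients, with 22 in each treatment group, will be enrolled", and the sample size text in section 11.0 has "22 in each group (two parallel treatment arms and two distinct control arms". The same paragraph also speaks of "statistically significant differences in time to closure outcomes between the three wound closure methods".

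For mHCS, AIRE and POSAS, the Data analysis plan in section 11.0 gives one sentence of method: "The differences in mHCS, AIRE, and POSAS scores between treatment groups will be tested through ANOVA tests and subsequent Tukey-HSD post-hoc tests". It lists seven patient covariates (age, gender, BMI, race, diabetes, smoking and alcohol). Surgeon is not among them.

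Section 4.0 says "Wound outcomes, both clinical and cosmetic, will be another primary endpoint for this study", whereas section 1.0 places cosmetic outcomes under the exploratory aims (Aim 3).

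**The concern.** The control technique is fixed by the surgeon, so staples and sutures never occur under the same surgeon. The design supports two randomised contrasts: PRINEO minus staples within one surgeon, and PRINEO minus sutures within the other. Tukey's method treats every pair of groups alike. It has no role with only two groups, so any grouping for which it is useful mixes surgeons.

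Two things are at stake. First, a difference between the surgeons' patients, technique or scoring could be reported as a difference between closure methods. Second, the contrasts that the trial was randomised to estimate are tested against a stricter threshold than they need. The closure-time t-tests are a separate matter and are not questioned here.

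**Working it through.** **The plan's own figure.** Section 11.0 gives a difference of 7.5 minutes, an SD of 8 minutes, d = 0.93, alpha 0.05, power 0.80 and 19 per group (76 in total). Here 7.5/8 = 0.9375. The two-sided normal formula n = 2(1.960 + 0.842)²/0.93² = 18.2 rounds up to 19, and 4 × 19 = 76. The exact t-test also gives 19 at d = 0.9375 (power 0.803), and 20 at d = 0.93 (power 0.797 at 19). The figure reproduces. It was derived for t-tests on closure time, not for Tukey tests on scores.

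**Counting pairs.** Four groups give 4 × 3/2 = 6 pairs. Two are within surgeon. The other 2 × 2 = 4 are between surgeons: staples vs sutures, each PRINEO arm vs the other surgeon's control (two pairs), and PRINEO vs PRINEO.

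**Cost in power.** Inputs are 22 per group and pooled error with 4 × 22 − 4 = 84 degrees of freedom. Critical t values are:
- six-pair Tukey: q(0.95; 4, 84)/√2 = 2.621, a per-pair alpha of 0.0104
- two contrasts at 0.025 each: 2.282
- unadjusted: 1.989

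Power is the noncentral-t probability beyond ±c, with noncentrality d√(22/2). At d = 0.93 the noncentrality is 0.93 × 3.317 = 3.08. No effect size is given for the scores, so a range is shown.

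| d | Tukey, six pairs | Two contrasts | Unadjusted |
|---|---|---|---|
| 0.5 | 0.175 | 0.272 | 0.374 |
| 0.8 | 0.516 | 0.645 | 0.746 |
| 0.93 | 0.678 | 0.787 | 0.862 |
| 1.25 | 0.933 | 0.967 | 0.984 |

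The effect detectable with 80% power is 1.05 SD under Tukey and 0.94 SD with two contrasts. For 80% power at d = 0.93, Tukey needs 28 per group and two contrasts need 23.

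**Surgeon difference read as a treatment difference.** This was simulated with 200,000 runs per setting, normal scores with SD 1, 22 per cell, no treatment effect and an assumed surgeon shift. The documents give no figure for the shift. Entries are the proportion of trials with a significant result under four-group Tukey.

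| Surgeon shift (SD) | 0 | 0.25 | 0.5 | 1.0 |
|---|---|---|---|---|
| Either randomised within-surgeon pair | 0.020 | 0.021 | 0.021 | 0.020 |
| Either PRINEO arm vs the other surgeon's control | 0.021 | 0.079 | 0.316 | 0.936 |
| Staples vs sutures | 0.010 | 0.040 | 0.175 | 0.757 |
| Any of the four between-surgeon pairs | 0.037 | 0.124 | 0.420 | 0.964 |

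Two within-surgeon contrasts at 0.025 each give 0.049 to 0.050 in every column, so they hold the 5% level whatever the surgeon shift.

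**If PRINEO is pooled to 44.** With surgeon shift s, the pooled PRINEO mean carries s/2, one control carries 0 and the other carries s. The two PRINEO-minus-control differences are therefore biased by +s/2 and −s/2. With the three-group critical value of 2.385, at least one false PRINEO-vs-control result occurs in 0.037 / 0.064 / 0.150 / 0.503 of trials at shifts of 0 / 0.25 / 0.5 / 1.0 SD. No pair is then a pure randomised contrast.

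**The case against.** On the four-group reading, which fits the stated 22 per group best, the randomised comparisons are sound. The four-cell ANOVA is the same fit as a surgeon-by-treatment model, the within-surgeon pairs are unbiased, and their false-positive rate is about 2%. Section 3.0 already tells the reader which comparisons are intended. This stands: under four groups the harm is lost power and a risk of misreading, not bias in the randomised pairs.

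The any-pair rate of 12%, 42% and 96% includes PRINEO vs PRINEO, which nobody could report as a difference between closure methods. This also stands, so the rate for PRINEO against the other surgeon's control is the better guide. Requiring a significant overall ANOVA first changes little: the any-pair rates become 11%, 40% and 96%.

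The plan sets no power target for the scores, d = 0.93 is borrowed, and two contrasts also fall just short of 0.80 at 22 per group. So the scores cannot be called underpowered against a stated target. What can be said is that all-pairs Tukey has less power than two planned contrasts at every effect size checked.

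The phrase about three closure methods concerns closure time, and nothing says that PRINEO will be pooled for the scores. The pooled result is therefore conditional, though the undefined groups leave it open.

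The blinded photograph rating in section 10.0 helps only in part. It covers six observer items of POSAS, not mHCS, AIRE or the patient part of POSAS, and it cannot remove differences in patients or surgical technique.

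**Conclusion.** The concern holds and should be fixed before analysis. The mismatch between within-surgeon randomisation and an all-pairs test with no surgeon term or named contrast rests on the text alone; the count of four non-randomised pairs in six rests on the four-group reading. The sizes depend on assumptions: normal scores with equal variance, an effect size borrowed from closure time, and a surgeon difference that the documents do not give. On those terms, power for a randomised contrast falls from 0.79 to 0.68 at d = 0.93, and a surgeon difference of 0.5 SD alone makes a PRINEO arm differ from the other surgeon's control in about a third of trials. The importance is limited by the conflicting status of the cosmetic scores, which are exploratory in section 1.0 and primary in section 4.0.

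**What to change.** In the Data analysis plan of section 11.0:
- Define the groups for mHCS, AIRE and POSAS as the four surgeon-by-treatment cells.
- Replace the Tukey step with two prespecified contrasts, PRINEO minus staples and PRINEO minus sutures, each within surgeon, from a model with surgeon, treatment and their interaction.
- Control multiplicity over those two contrasts only, for example by Holm or at 0.025 each.
- State that pooled PRINEO will not be compared with one surgeon's controls, and that any staples-vs-sutures figure for the scores is descriptive and non-randomised.

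The cost is wording only; patients, data and software are unchanged. The plan gives up a formal staples-vs-sutures test of the scores. The design cannot support that test, and Aims 2 to 4, which set PRINEO against each control, do not claim it.
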